Was the Amgen product (o If yes, provide product Did the subject withdraw fr Did the subject withdraw fr Did the subject withdraw fr Did the subject withdraw fr Did the subject withdraw fr Pregnant female's LMP mm Estimated date of delivery mm If N/A, date of termination (Has the pregnant female alread If yes, provide date of deli Was the infant healthy? Yes f any Adverse Event was experi- f any Adverse Event was experi- f any Adverse Event was experi- f any Adverse Event was experi-	or study drug) discontinu t (or study drug) stop da om the study? Yes ON (actual or planned) mm dy delivered? Yes very: mm 1/dc is No Unknow rienced by the infant, pr	ied? Yes intermined? No No yyyy Ur yyyy Ur ↓ / dd ↓ No Unkno d ↓ / yyyy vn N/A rovide brief details:	No Vo Vyyyyy Nknown Nknown NA Vyyyy NA N/A	mm _ //d _ /yyyy
Was the Amgen product (o If yes, provide product Did the subject withdraw fr Did the subject withdraw fr Did the subject withdraw fr Did the subject withdraw fr Did the subject withdraw fr Pregnant female's LMP mm Estimated date of delivery mm If N/A, date of termination (Has the pregnant female alread If yes, provide date of deli Nas the infant healthy? Yes f any Adverse Event was exper- f any Adverse Event was exper- f any Adverse Event was exper- com Completed by: Print Name:	or study drug) discontinu t (or study drug) stop da om the study? Yes ON (actual or planned) mm dy delivered? Yes very: mm // dc : No Unknow rienced by the infant, pr	led? Yes intermined? No No YyyyUr yyyyUr yyyyUr vn No Unkno d v/yyyy vn N/A rovide brief details: Tit Da	No I/yyyyy hknown hknown N / yyyy wn NA	mm _ √/dd _ /yyyy

Superseding Amendment 1

A Double-blind, Randomized, Placebo-Controlled, Multicenter Study to Evaluate Safety and Efficacy of Evolocumab (AMG 145) in Combination With Statin Therapy in Diabetic Subjects With Hyperlipidemia or Mixed Dyslipidemia

Evolocumab (AMG 145)

Amgen Protocol Number Evolocumab 20120119

Superseding Amendment 1 Date: 07 February 2014

Rationale:

This document provides the rationale and detailed list of changes for Superseding

Amendment 1, dated 07 February 2014, from the original protocol, dated

22 February 2013.

The purpose of the amendment is to:

Add mixed meal tolerance testing (MMTT) with 1 timepoint for all subjects, and optional MMTT substudy with 2 additional timepoints for approximately 240 subjects

Replace the Amgen product number "AMG 145" with the generic name "evolocumab"

Update the contraception language

Minor updates and clarifications, including clarification that atorvastatin in this study is background therapy

Amendment 1

A Double-blind, Randomized, Placebo-Controlled, Multicenter Study to Evaluate Safety and Efficacy of Evolocumab (AMG 145) in Combination With Statin Therapy in Diabetic Subjects With Hyperlipidemia or Mixed Dyslipidemia

Evolocumab (AMG 145)

Amgen Protocol Number Evolocumab 20120119

Amendment 1 Date: 10 December 2013

Rationale:

This document provides the rationale and detailed list of changes for Amendment 1, dated 10 December 2013, from the original protocol, dated 22 February 2013.

The purpose of the amendment is to:

- Add mixed meal tolerance testing (MMTT) with 1 timepoint for all subjects
- Replace the Amgen product number "AMG 145" with the generic name "evolocumab"
- Update the contraception language
- Minor updates and clarifications

11.	Chang	jes From F	Protocol-spe	ecified Analyses	31
12.	Literat	ure Citatio	ons / Refere	nces	32
13.	Appendices				

List of Tables

Table 1.	Imputation Rules for Incomplete	Dates	20
Table 2.	Key Efficacy Analyses Summary	Table	25

List of Appendices

Appendix A.	Analytical Study Week/Time Point Assignments	34
Appendix B.	Common Terminology Criteria for AEs (CTCAE)	35
Appendix C.	Lipid Modifying Background Therapy Intensity	36

Table of Abbreviations

Abbreviation or Term	Definition/Explanation
ADE	Adverse device effect
AE	Adverse event
ALT (SGPT)	Alanine aminotransferase (serum glutamic-pyruvic transaminase)
ApoA1	Apolipoprotein A-1
ApoB48	Apolipoprotein B48
ApoB100	Apolipoprotein B100
AST (SGOT)	Aspartate aminotransferase (serum glutamic-oxaloacetic transaminase)
BMI	Body mass index
BP	Blood pressure
CAS	Completer analysis set
СК	Creatine kinase
CHD	Coronary heart disease
СМН	Cochran-Mantel-Haenszel
CPMS	Clinial Pharmacology Modeling and Simulation
CRP	C-reactive protein
CSR	Clinical study report
CTCAE	NCI Common Terminology Criteria for AEs
DBP	Diastolic blood pressure
DQR	Data quality review
DMC	Data monitoring committee
EAS	European Atherosclerosis Society
ECG	Electrocardiogram
eCRF	Electronic case report form
EOS	End-of-study
ESC	European Society of Cardiology
FAS	Full analysis set
GSO-DM	Global Study Operations – Data Management
HDL-C	High density lipoprotein cholesterol
HeFH	Heterozygous familial hypercholesterolemia
hsCRP	High sensitivity CRP
IBG	Independent Biostatistical Group
ІСН	International Conference on Harmonization
IEC	Independent ethics committee
IRB	Institutional Review Board

Abbreviation or Term	Definition/Explanation
IP	Investigational product
IVRS/IWRS	Interactive Voice Response System / Interactive Web Response System
LDL-C	Low-density lipoprotein cholesterol
LDLR	LDL receptor
LFT	Liver function test
Lp(a)	Lipoprotein(a)
LSP	Lipid stabilization period
LSAS	Lipid stabilization analysis set
MedDRA	Medical dictionary for regulatory activities
MMTT	Mixed meal tolerance test
MOI	Medications of interest
NCEP	National Cholesterol Education Program
PCSK9	Proprotein convertase subtilisin/kexin type 9
PK	Pharmacokinetics
PKS	Pharsight knowledgebase server
PO	Oral administration
POSTD	Dose date of statin therapy
QM	Every 4 weeks
Q2W	Every 2 weeks
QD	Each day
SAE	Serious adverse event
SAP	Statistical analysis plan
SBP	Systolic blood pressure
SC	Subcutaneous
SCIPD	Subcutaneous investigational product
SD	Standard deviation
SE	Standard error
TEAE	Treatment-emergent adverse event
ULN	Upper limit of normal
VLDL-C	Very low-density lipoprotein cholesterol
WHODRUG	World Health Organization Drug

1. Introduction

The purpose of this Statistical Analysis Plan (SAP) is to provide details of the statistical analyses that have been outlined within the protocol for evolocumab Study 20120119 amendment 3 dated 11 November 2015. The scope of this plan includes the final analyses that are planned and will be executed by the Biostatistics department unless otherwise specified.

2. Objectives

2.1 Primary

To evaluate the effect of 12 weeks of subcutaneous (SC) evolocumab every 2 weeks (Q2W) and monthly (QM), in combination with oral (PO) atorvastatin daily (QD), compared with placebo Q2W and QM, in combination with PO atorvastatin QD, on percent change from baseline in low-density lipoprotein cholesterol (LDL-C) in diabetic subjects with hyperlipidemia or mixed dyslipidemia.

2.2 Secondary

- To evaluate the safety and tolerability of SC evolocumab Q2W and QM in combination with atorvastatin QD, compared with placebo Q2W and QM, in combination with atorvastatin QD, in diabetic subjects with hyperlipidemia or mixed dyslipidemia
- To assess the effects of 12 weeks of SC evolocumab Q2W and QM in combination with atorvastatin QD, compared with placebo Q2W and QM, in combination with atorvastatin QD, on change from baseline in LDL-C, and percent change from baseline in non-high-density lipoprotein cholesterol (non-HDL-C), apolipoprotein B100 (ApoB100), total cholesterol, total cholesterol/HDL-C ratio, ApoB100/Apolipoprotein A-1 (ApoA1) ratio, lipoprotein(a) [Lp(a)], triglycerides, very low-density lipoprotein cholesterol (VLDL-C), and HDL-C in diabetic subjects with hyperlipidemia or mixed dyslipidemia
- To assess the effects of 12 weeks of SC evolocumab Q2W and QM in combination with atorvastatin QD, compared with placebo Q2W and QM, in combination with atorvastatin QD, on percent of subjects attaining LDL-C < 70 mg/dL (1.8 mmol/L) in diabetic subjects with hyperlipidemia or mixed dyslipidemia

2.3 Tertiary

- To assess the treatment effects of 12 weeks SC evolocumab Q2W and QM in combination with atorvastatin QD, compared with placebo Q2W and QM, in combination with atorvastatin QD, on percent change from baseline of ApoA1 in diabetic subjects with hyperlipidemia or mixed dyslipidemia
- to characterize evolocumab PK exposure

2.4 Exploratory

- To describe the effects over time of SC evolocumab Q2W and QM in combination with atorvastatin QD, compared with placebo Q2W and QM, in combination with atorvastatin QD, on change from baseline in proprotein convertase subtilisin/kexin type 9 (PCSK9) levels and on change from baseline and percent change from baseline of LDL-C, total cholesterol, non-HDL-C, ApoB100, total cholesterol/HDL-C ratio, ApoB100/ApoA1 ratio, triglycerides, VLDL-C, HDL-C, ApoA1, and Lp(a), and categorical change from baseline in high sensitivity C-reactive protein (hsCRP) in diabetic subjects with hyperlipidemia or mixed dyslipidemia
- To explore the effect of SC evolocumab Q2W and QM in combination with atorvastatin QD, compared with placebo Q2W and QM, in combination with atorvastatin QD, on fasting and postprandial plasma laboratory parameters of interest
- To investigate the relationship between novel and established biochemical cardiovascular and lipid biomarkers and effects of evolocumab
- To investigate potential correlations of study data including the subject response to evolocumab with genetic variation in markers of PCSK9 signaling, low-density lipoprotein receptor (LDLR) turnover, cholesterol metabolism, inflammation, and plaque stability in subjects consenting to the optional pharmacogenetics analysis
- To explore evolocumab population pharmacokinetics in diabetic subjects
- To explore evolocumab exposure/response relationships in diabetic subjects

3. Study Overview

3.1 Study Design

This is a phase 3, multicenter, double-blind, randomized, stratified, placebo-controlled study of evolocumab for diabetic subjects with hyperlipidemia or mixed dyslipidemia. After undergoing screening procedures, including laboratory assessments and a screening placebo injection, approximately 900 subjects meeting eligibility criteria and completing at least 4 weeks of lipid stabilization on atorvastatin 20 mg QD will be randomized 2:2:1:1 into the following treatment arms:

- evolocumab SC 140 mg Q2W and atorvastatin PO 20 mg QD
- evolocumab SC 420 mg QM and atorvastatin PO 20 mg QD
- placebo SC Q2W and atorvastatin PO 20 mg QD, or
- placebo SC QM and atorvastatin PO 20 mg QD.

The sample size for each of the evolocumab plus atorvastatin dosing regimens will be approximately 300 subjects. The sample size for each of the placebo plus atorvastatin dosing regimens will be approximately 150 subjects.

Randomization into the 4 treatment groups will be stratified by entry statin therapy (no statin use vs non-intensive statin use vs intensive statin use [see Appendix C]) and by

the site's geographic region (China, Korea, other countries). Treatment and follow-up period will be 12 weeks with an additional phone call or other subject contact at week 14 for subjects receiving investigational product (IP) Q2W.

Evolocumab and placebo SC will be administered at the study site or appropriate noninvestigator site settings, e.g., at the subject's home, per protocol Section 6 and Section 7 by spring-based prefilled autoinjector/pen (prefilled Al/Pen) for subjects receiving IP Q2W and by 3.5 mL Personal Injector for subjects receiving IP QM. The dose frequencies of Q2W and QM will not be blinded but the identity of IP (evolocumab or matching SC placebo) will be blinded. Post-IP treatment central laboratory results of the lipid panel, ApoA1, ApoB100, ApoB48, free fatty acids, chylomicrons, lipoprotein(a), PCSK9, insulin, proinsulin, C-peptide, glucagon, IL-6, adiponectin, vitamin E, PK, and high sensitivity C-reactive protein (hsCRP) will be blinded until unblinding of the clinical database and will not be reported to the investigator post-screening. Investigators should not perform non-protocol testing of these analytes during a subject's study participation and until at least 12 weeks after last IP administration, or the subject's end of study, whichever is later.

The study includes collection of biomarker samples and, where approved by the institutional review board and/or independent ethics committee (IRB/IEC) and applicable regulatory and other authorities, subjects will be invited to consent to pharmacogenetics analyses. All subjects will complete a mixed meal tolerance test (MMTT) at the day 1 and week 12 study visits with a fasting blood collection (0 hours) and 1 postprandial blood collection 2 hours (± 10 min) after the meal and up to approximately 240 subjects will participate in a MMTT Extended Timepoints Substudy with 2 additional postprandial blood draws at 1 hour (± 10 min) and 3 hours (± 10 min) after the meal. End of study (EOS) for subjects on QM IP is at the week 12 visit. EOS for subjects on Q2W IP is by contact (e.g., phone call) from the site at week 14 for any potential adverse events (AEs), adverse device effects (ADEs), and serious AEs (SAEs). Subjects will be encouraged to complete all planned visits regardless of their adherence to IP administration. Accumulating safety and other data will be reviewed by an independent external Data Monitoring Committee (DMC). Where analyte concentrations are provided in mmol/L, it is for investigator convenience.

Conventional concentrations (mg/mL) will be used for the protocol, including for eligibility determination.

The overall study design is described by a study schema at the end of the protocol synopsis section. Detailed study procedures are provided in Protocol Section 7.

The study endpoints are defined in Section 4.1

3.2 Sample Size

The sample size is 300 subjects for each of the evolocumab SC in combination with atorvastatin arms, and 150 subjects for each of the placebo in combination with atorvastatin arms. The sample size should provide adequate power to determine the superiority of evolocumab in combination with atorvastatin to placebo in combination with atorvastatin as measured by the co-primary endpoints in both dose frequencies using the full analysis set (FAS). The primary analysis will require the tests of each co-primary endpoint to be significant at a level of 0.05 (Section 10.1). From the global phase 2 studies in the evolocumab program, the treatment effect measured as the mean of week 10 and week 12 were as large or larger than week 12 and highly correlated (> 85%) with ones at week 12. From the global phase 2 study 20110155, the treatment effects (on top of stable background statin therapy) of evolocumab compared to placebo for 140 mg Q2W and 420 mg QM in the mean percent change from baseline in LDL-C are -66.10 (95% CI [-71.48,-60.72]) and -50.33 (95% CI [-56.04,-44.62]) at week 12, respectively and the observed evolocumab dose group means in the type II diabetes mellitus cohort were comparable to the overall population. The power calculation is derived assuming a treatment effect in the percent reduction of LDL-C of at least 35% at week 12 in each dose frequency, with a common standard deviation (SD) of 20%. It is assumed that approximately 15% of subjects randomized into IP will end IP early, thus attenuating the treatment effects. It is assumed there will be no treatment effect differences among treatment groups after these subjects end IP early. After accounting for treatment attenuation due to early IP termination, the assumed treatment effect is a 30% reduction in LDL-C with a common SD of 30%. Assuming 2% of randomized subjects do not receive any IP, the planned sample size will provide at least 99% power in testing the superiority of evolocumab in combination with atorvastatin to placebo in combination with atorvastatin at week 12 in each dose frequency. Therefore, the sample size as planned will provide at least 98% (99% x 99%) power for the co-primary endpoints in each of the dose frequencies.

Since the testing statistics from the Q2W and QM groups are independent, there is approximately a 96% (98% x 98%) chance to show the superiority of both dose frequencies for the co-primary endpoints.

Sample size assumptions, such as the missing value rate, will be monitored by the study team while maintaining study blind.

The power calculation is derived using nQuery version 7.01.

4. Study Endpoints and Covariates

4.1 Study Endpoints

4.1.1 Co-Primary Efficacy Endpoint

- Mean percent change from baseline in LDL-C at weeks 10 and 12
- Percent change from baseline in LDL-C at week 12

4.1.2 Co-Secondary Efficacy Endpoints

Co-secondary efficacy endpoints are (1) the mean of weeks 10 and 12 and (2) week 12 for:

Tier 1 endpoints

- Change from baseline in LDL-C
- Percent change from baseline in non-HDL-C
- Percent change from baseline in ApoB100
- Percent change from baseline in the total cholesterol
- Percent change from baseline in the total cholesterol/HDL-C ratio
- Percent change from baseline in ApoB100/ApoA1 ratio
- Achievement of target LDL-C < 70 mg/dL (1.8 mmol/L)

Tier 2 endpoints

- Percent change from baseline in Lp(a)
- Percent change from baseline in triglycerides
- Percent change from baseline in HDL-C
- Percent change from baseline in VLDL-C

4.1.3 Co-Tertiary Efficacy Endpoints

• Mean percent change from baseline at weeks 10 and 12 and percent change from baseline at week 12 in ApoA1

4.1.4 Exploratory Endpoints

- Subject incidence of non-coronary revascularization
- Change and percent change from baseline at each scheduled assessment in each of the following parameters:
 - LDL-C
 - total cholesterol
 - non-HDL-C

- ApoB100
- total cholesterol/HDL-C ratio
- ApoB100/ApoA1 ratio
- VLDL-C
- HDL-C
- ApoA1
- triglycerides
- Lp(a)
- hsCRP at each scheduled assessment
- HbA1c at each scheduled assessment
- PCSK9 change from baseline at each scheduled assessment
- Fasting and postprandial laboratory parameters of interest (including MMTT Extended Timepoints Substudy assessments)

4.1.5 Safety Endpoints

- Subject incidence of treatment-emergent adverse events
- Safety laboratory values and vital signs at each scheduled assessment
- ECG parameters (such as RR, PR, QRS, QT and QTc intervals) at each scheduled assessment
- Incidence of anti-evolocumab antibody (binding and neutralizing) formation

4.1.6 Pharmacokinetics Endpoints

• Serum concentration of evolocumab at selected time points

4.2 Planned Covariates

Baseline covariates include, but are not limited to:

Stratification factors

- Statin therapy at study entry (no statin use vs non-intensive statin use vs intensive statin use [see Appendix C]
- Site's geographic region (China, Korea, other countries)

Baseline characteristics

- Age
- Sex
- Race
- Baseline LDL-C
- Family history of premature coronary heart disease (yes, no)
- Baseline PCSK9

- Body Mass Index
- Hypertension (yes, no)
- Current smoker (yes, no)
- Baseline CHD risk factors \geq 2 (yes, no)
- Triglycerides

5. Hypotheses and/or Estimations

Hypothesis testing between IP treatment groups will be conducted separately by SC IP dose frequency.

The primary statistical hypothesis of the co-primary endpoints is as follows:

Within each randomized SC IP dose frequency, the null hypothesis is that there is no mean difference in the mean percent change from baseline at weeks 10 and 12 or in the percent change from baseline at week 12 in LDL-C between evolocumab and placebo in combination with atorvastatin QD, and the alternative hypothesis is that a mean difference does exist.

6. Definitions

6.1 Study Time Points

Enrollment Date

Enrollment Date is the same as the start date of lipid stabilization as the date collected on the eCRF.

Randomization date

Randomization date is defined as the date subject was allocated to a treatment group in the interactive voice response system or interactive web response system (IVRS/IWRS) as recorded on the eCRF.

First Dose Date of SC Investigational Product (First SCIPD)

For each subject, the First Dose Date of SC Investigational Product is defined as the first administration date of the SC IP as recorded on the IP administration eCRF.

First Dose Date of Atorvastatin Therapy (First POSTD)

For each subject, the First Dose Date of Atorvastatin Therapy is defined as the first start date of the study-assigned atorvastatin therapy as recorded on the non-IP administration eCRF.

Study Day 1

For each subject, Study Day 1 is defined as the first day of investigational product (IP) administration.

Study Day

For each subject, and for a given date of interest, study day is defined as the number of days since Study Day 1:

Study day = (date of interest – Study Day 1 date) + 1.

If the date of interest is prior to the Study Day 1:

Study day = (date of interest – Study Day 1 date), so that the day prior to Study Day 1 is study day - 1.

Last Dose Date of SC Investigational Product (Last SCIPD)

For each subject, the Last Dose Date of SC Investigational Product is defined as the date of the last administration of the SC IP.

Last Dose Date of Atorvastatin Therapy (Last POSTD)

For each subject, the Last Dose Date of Atorvastatin Therapy is defined as the last stop date of the atorvastatin therapy.

End of IP Admin Date

End of IP Admin for each subject is defined as the date the decision was made to end IP as recorded on the End of IP eCRF page.

End of Study (EOS) Date

For each subject, the End of Study Date is the date recorded on the End of Study eCRF.

Study End Date

The Study End Date is the last EOS date of all randomized subjects.

6.2 Demographics and Baseline Related Definitions

Age

Subject age at enrollment will be collected in years on the eCRF.

Baseline Lipid and Lipid-related Parameters

Baseline values for fasting lipids (total cholesterol, HDL-C, LDL-C, VLDL-C, non-HDL-C and triglycerides), ApoA1, ApoB100, ApoB48, hsCRP, Lp(a) and their derived parameters (e.g., ratio between them) are defined as the fasting concentrations

measured through central lab on Study Day 1. If for any reason a concentration for a parameter is not observed on Study Day 1, the closest prior to Study Day 1 measurement for the parameter to Study Day 1 will be used.

Body mass index (BMI)

Subject's BMI will be derived in kg/m² in the clinical database.

Other Baseline Values

For ECG data, the baseline value is defined as the nonmissing triplicate average of 3 (or all available) readings taken on Study Day 1. If the Study Day 1 reading is missing, the closest nonmissing triplicate reading prior to Study Day 1 will be used as the baseline.

For PCSK9, the baseline value is defined as the last non-missing value collected prior to or on Study Day 1, but must be prior to first IP administration.

For all other variables, the baseline value is defined as the last non-missing value collected prior to or on Study Day 1.

Change (Absolute Change) from Baseline

The arithmetic difference between a post-baseline value and baseline for a given time point:

Change (absolute change) from baseline = (post-baseline value – baseline value)

Percent Change from Baseline

The percent change from baseline for a given variable at a given time point is defined as:

[(value at a given time point – baseline value) / baseline value] x 100%

Baseline CHD Risk Factors

A subject will be categorized as having 2 or more CHD Risk Factors (Y/N) from the list of the modified NCEP ATP III risk factors:

- current cigarette smoking,
- hypertension,
- type II diabetes mellitus,
- family history of premature CHD as recorded on the eCRF, and
- low HDL-C defined as baseline HDL-C < 40 mg/dL in males and < 50 mg/dL in females.

Systematic Coronary Risk Estimation (SCORE) Categories

The SCORE system estimates the 10 year risk of a first fatal atherosclerotic event, whether heart attack, stroke, or other occlusive arterial disease, including sudden cardiac death (ESC/EAS 2011). The SCORE risk estimates will be computed from the high and low risk region tables based on sex and baseline smoking status, systolic blood pressure, total cholesterol and age.

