7. STUDY PROCEDURES

7.1 Schedule of Assessments

	Screen & Lipid Stabilization			Treatment Period							Phone
Study Day / Week / Other Timepoint ^a	Screen	Enroll Start Atorva	End of Lipid Stabil	D1 Visit Rand.	W2 Visit	W4	W6	W8 Visit	W10 Visit	W12 Visit (QM EOS)	W14 ^b Q2W EOS
General Procedures											
Informed consent	Х										
Medical history	Х										
Vital Signs (sitting BP, HR)	Х			Х	Х				Х	Х	
Review for AEs/ADEs/SAEs	Xc		Xc	Х	Х	(X) ^d	(X) ^d	Х	Х	Х	Х
Concomitant therapy	Х		Х	Х	Х			Х	Х	Х	
Dietary instruction	Х			Х	Х			Х	Х		
Physical exam	Х									Х	
Body weight, waist circumference				Х						Х	
Body height	Х										
12 lead ECG	Х			Х					Х	Х	
Randomization				Xe							
Central Laboratory											
Fasting lipids ^g	Х		Х	Х	Х			Х	Х	Х	
ApoA1, ApoB100, Lp(a)				Х					Х	Х	
PK (evolocumab), PCSK9				Х	Х			Х	Х	Х	
Chemistry, including fasting glucose ^g	Х		Х	Х				Х		Х	
Hematology	Х			Х				Х		Х	
hsCRP				Х						Х	
HbA1c	Х									Х	
TSH	Х										
MMTT: Plasma glucose, insulin, proinsulin, C-peptide, free fatty acids, glucagon, lipids, chylomicrons, ApoB48, IL-6, adiponectin, vitamin E, measured after $a \ge 9$ hour fast just prior to a standardized meal (0 minutes), and then 120 minutes after ^h				Х						x	
MMTT Extended Timepoints Substudy: Same analytes as for MMTT, measured at additional timepoints (60, 180 minutes) in subjects participating in the substudy) ^h				Х						X	
Biomarkers (blood) ^{ji}				Х						Х	
Anti-evolocumab antibodies				Х						Х	
HCV testing ⁱ	Х										
HCV viral load ¹				X	Х			X		X	
Serum pregnancy; FSH ^k	Х		X							X	
Urine pregnancy				X	Х			Х			
Urinalysis, urine microalbumin				Х						Х	

Table 1. Schedule of Assessments

Footnotes defined on last page of this table.

Page 1 of 2

	Screen & Lipid Stabilization			Treatment Period							Phone
Study Day / Week / Other Timepoint ^a	Screen	Enrol Start Atorva	End of Lipid Stabil	D1 Visit Rand.	W2 Visit	W4	W6	W8 Visit	W10 Visit	W12 Visit (QM EOS)	W14 ^b Q2W EOS
Steroid analytes				Х						Х	
Investigational Product											
Screening placebo injection	Х										
Atorvastatin dispensation ^m	Х	Х	Х	Х	Х			Х			
Atorvastatin tablet count ^m	Х		Х	Х	Х			Х		Х	
Al/Pen / 3.5 mL Personal Injector Instruction	Х			Х	Х			Х			
Al/Pen / 3.5 mL Personal Injector dispensation					Х			Х			
Al/Pen / 3.5 mL Personal Injector reconciliation								Х			
Q2W IP on-site				Х	Х			Х	Х		
QM IP on-site				Х				Х			
Q2W IP on-site or in non-investigator site setting						Х	Х				

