If a fasting sample could not be obtained at the initial screening visit and the other screening laboratory assessments confirm eligibility for the study, fasting lipid and glucose samples to determine eligibility must be obtained before changing or discontinuing the current lipid lowering treatment.

Eligible subjects will be enrolled (Section 5) and will start their lipid stabilization on 20 mg QD atorvastatin background therapy. If during lipid stabilization a subject is found not to tolerate the assigned atorvastatin background therapy, the subject should not continue but should early terminate the study. In contrast, if intolerance is discovered after randomization to IP, the subject should continue the study until completion. Before reducing or discontinuing treatment with atorvastatin, please contact the Amgen medical monitor. All prohibited lipid lowering therapy (see exclusion 208 and Section 6.9) must be discontinued at the start of lipid stabilization.

After \geq 4 weeks of lipid stabilization, subjects will return to the study site for the end of lipid stabilization assessments.

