7.2.1.3 Randomization

Subjects who continue to meet all eligibility criteria at the end of lipid stabilization will be randomized and will return to the study site again for day 1 procedures while continuing their atorvastatin background treatment. Randomization should be on day 1 or as close as possible and not earlier than maximally 5 days prior. Subjects can only be randomized 1 time for this study.

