7.7.5 Lipid Measurements

Only the screening LDL-C concentration will be reported to the site for the eligibility decision. Central laboratory results of the lipid panel, as well as ApoA1, ApoB, and lipoprotein(a) (and PCSK9 and hsCRP) will be blinded post-treatment until unblinding of the clinical database. and will not be reported to the investigator post-screening. In addition, investigators and staff involved with this trial and all medical staff involved in the subject's medical care should refrain from obtaining lipid panels from randomization until at least 12 weeks after the subject's last administration of IP or until the subject ends the study, whichever is later (to avoid potential unblinding). If a lipid panel is

drawn, all reasonable steps must be undertaken to avoid informing the subject and study personnel of the results.

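### Baseline for the fasting-panel lipids could be the mean of two on-atorvastatin samples already scheduled, a nearly free gain in precision

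*SAP*

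**What the plan says.** SAP 6.2 defines baseline for all lipid and lipid-related parameters as the fasting values "measured through central lab on Study Day 1". An earlier sample enters only as a fallback: "If for any reason a concentration for a parameter is not observed on Study Day 1, the closest prior to Study Day 1 measurement" is used. Percent change is the post-baseline value minus baseline, divided by baseline, so baseline appears in numerator and denominator.

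Protocol 7.2.1.2 says that after at least 4 weeks of stabilization "subjects will return to the study site for the end of lipid stabilization assessments". Protocol 7.2.1.3 makes Day 1 a further visit: subjects "will return to the study site again for day 1 procedures while continuing their atorvastatin background treatment". In Table 1 the fasting-lipids row is marked at screening, end of stabilization, Day 1 and weeks 2, 8, 10 and 12. The row for ApoA1, ApoB100 and Lp(a) starts at Day 1, as does the hsCRP row.

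The repeated measures model in SAP 10.5.1.1 lists treatment, stratification factors, visit and treatment by visit. Baseline is not a listed term.

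**The concern.** The end-of-stabilization and Day 1 panels are both fasting, central-laboratory, on-statin and pre-IP. The plan measures baseline twice for the panel lipids and then uses one measurement. The error in that one value enters weeks 10 and 12 alike, so averaging those weeks cannot remove it, and no baseline term in the model absorbs it.

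The earlier panel does not look distorted by selection. The LDL-C and triglyceride limits in Protocol 4.1.1 apply at screening, and Protocol 7.7.5 states: "Only the screening LDL-C concentration will be reported to the site for the eligibility decision".

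What is at stake is precision for endpoints with modest effects. Triglycerides, VLDL-C and HDL-C are three of the four tier 2 endpoints, tested by Hochberg at 0.025, or at 0.02 if tier 1 is not fully significant. Neither document states power for them.

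A smaller point is that the fallback has no on-atorvastatin limit. If both later panels were missing it would reach the screening sample, drawn before study atorvastatin, and percent change would then mix the statin effect with the IP effect.

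**Working it through.** **The plan's own figure.** Inputs from SAP 3.2 are a difference of 30, SD 30, 300 vs 150 randomized and 2% never dosed, which leaves 294 vs 147. SE = 30 × √(1/147 + 1/294) = 3.03 and 30/3.03 = 9.9, so two-sided power at 0.05 is above 99.99%. The stated minimum of 99% is met. It would need only 28 placebo and 56 evolocumab subjects.

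**LDL-C after averaging.** Let R be the on-treatment/baseline ratio, CVw the within-subject CV and ρ the correlation of the two baseline errors. By the delta method, averaging removes (R × CVw)² × (1 − ρ)/2 from the variance of percent change. CVw and ρ are assumptions. At CVw 10%, ρ = 0 and the pre-attenuation SD of 20% (variance 400):
- placebo, R = 1: 10²/2 = 50, or 12.5% of 400
- evolocumab at a 35% reduction, R = 0.65: 6.5²/2 = 21, or 5.3% of 400

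SE of the treatment difference, ρ = 0:

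| Planning SD | One baseline | Two, CVw 5% | Two, CVw 10% | Two, CVw 15% |
|---|---|---|---|---|
| 20% (R = 0.65) | 2.02 | 2.00 | 1.92 | 1.78 |
| 30% (R = 0.70) | 3.03 | 3.01 | 2.96 | 2.87 |

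The SE falls by 1.3-12.1% in the first row and 0.6-5.3% in the second, and by about half that at ρ = 0.5. Power is above 99.99% throughout.

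**Panel lipids in general.** On the log scale, with within-subject variance σ², response variance τ² and independent errors:
- week 12: 2σ² + τ² becomes 1.5σ² + τ²
- mean of weeks 10 and 12: 1.5σ² + τ² becomes σ² + τ²

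With τ = 0 the reductions are 0.5/2 = 25% and 0.5/1.5 = 33%. With ρ = 0.5 the saving is 0.25σ² instead of 0.5σ².

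A log-normal simulation of percent change itself (600,000 subjects, between-subject log SD 0.4) gave these variance reductions over week 12 and the mean of weeks 10 and 12:

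| Within-subject log SD | Response log SD | ρ = 0 | ρ = 0.5 |
|---|---|---|---|
| 0.10 | 0.10-0.20 | 9-21% | 5-11% |
| 0.20-0.30 | 0-0.20 | 21-40% | 11-21% |

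**Power illustration.** For one test with 70% power at two-sided 0.025, the expected z is 2.241 + 0.524 = 2.766. A variance ratio r changes power to Φ(2.766/√r − 2.241).
- ρ = 0: r = 0.91 gives about 75%, and r = 0.60 gives about 91%.
- ρ = 0.5: r = 0.95 gives about 72%, and r = 0.79 gives about 81%.

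**Mean shift.** A noisy denominator raises mean percent change. At noise 0.20 with no effect and no response variation the shift is exp(0.04) − 1 = 4.1 points with one baseline and about 2.0 with two. Between arms it mostly cancels: a 10-point difference becomes 10 × 1.041 = 10.4, a change of 0.4 point.

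**The case against.** The strongest reply is that nothing here is wrong. The definition is explicit, prespecified and the same in every arm; type I error is intact and co-primary power cannot be improved to any practical extent. That stands.

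The size also rests on inputs the documents do not contain. The within-subject SD, the response SD and the error correlation are all assumed. Noise of 0.20 or more does not fit LDL-C: it alone implies a placebo percent-change SD of 30%, against the planning SD of 20%, which caps noise near 0.14. The power figures describe a single test, whereas tier 2 uses a union-intersection p-value per lipid and then Hochberg across four lipids. These objections also stand, so the figures are ranges for illustration.

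Three stronger readings are tempting and unsupported.
- A reader might infer that every percent change is affected. ApoB100, ApoB100/ApoA1, Lp(a) and ApoA1 have no second scheduled baseline sample, and achievement of LDL-C below 70 mg/dL uses no baseline.
- A reader might infer that the treatment effect is biased upward. The shift is within each arm and largely cancels in the comparison.
- A reader might infer that pre-statin baselines will often enter. Protocol 7.2.2 requires a non-fasting Day 1 visit to be repeated, and Protocol 5.1 places randomization after the end-of-stabilization assessments. Both panels would have to be missing.

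One practical objection must be met in the fix. Fasting is required before each visit (Protocol 7.2), but the explicit rules for a non-fasting subject cover initial screening, Day 1 and later visits, not the end-of-stabilization visit. Triglycerides may also be retested during screening (Protocol 7.2.1.4).

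**Conclusion.** This is a cheap improvement, not an error or a contradiction. For the panel lipids, averaging the two scheduled baselines would cut the variance of percent change by about 9-40% with independent baseline errors and about 5-21% at correlation 0.5. This assumes within-subject log SD 0.10-0.30 and response log SD 0.10-0.20 (0-0.20 when noise is 0.20 or more), and that both panels measure the same stable on-statin level. Closely spaced draws would push the gain toward the lower range.

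The benefit would fall mainly on triglycerides, VLDL-C and HDL-C. The documents do not support saying that baseline noise decides significance there, because they give no effect size or SD for these endpoints. The co-primary conclusion does not depend on this choice.

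**What to change.** In SAP 6.2, before unblinding:
- For LDL-C, total cholesterol, HDL-C, triglycerides, VLDL-C, non-HDL-C and the total cholesterol/HDL-C ratio, define baseline as the mean of the end-of-lipid-stabilization and Day 1 fasting values, or the available one if only one exists.
- If a visit was retested, use the last fasting value at that visit. Exclude non-fasting samples.
- Limit the fallback to samples taken after at least 4 weeks on study atorvastatin.
- Keep Day 1 alone for ApoA1, ApoB100, ApoB100/ApoA1, Lp(a) and hsCRP.

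The cost is one definition and its programming, with no new sample or visit. Panel lipids and apolipoproteins would have different baseline definitions, including within tier 1, and the median-baseline subgroups would shift slightly. If the sponsor regards this as a change to a protocol-specified analysis, it belongs in SAP Section 11.
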